Bomedemstat Dosing: All patients will be dosed with bomedemstat daily with dose-titration contingent on the Titration Assessment performed at every TP visit. Patients receiving their first extension study dose with no interruption in dosing will have a Titration Assessment performed at the Transition Visit to determine if a titration is needed. Patients requiring an interruption in dosing will have a Titration Assessment performed at the Transition Visit to determine if they will commence at the same daily dose of bomedemstat being taken at the conclusion of their feeder study or if a down-titration or dose hold is needed (up-titrations are not permitted). Titration targets and rules, specific to the underlying MPN, are detailed in the Study Reference Manual, Pharmacy Manual, and Appendix 16.1.3 and 16.1.4. The upper limit for titration is 6 mg/kg/day.

Study Assessments: The key study assessments outlined below are also summarized in Study Assessments, Section 9, and in the Schedule of Assessments, Section 16.1.

\*Patients entering the extension study at the final visit of the feeder study will undergo the asterisked procedures in association with the feeder study; the assessments should not be duplicated. Patients entering the extension study that require interruption of dosing must undergo the asterisked procedures.

Limited Physical Examinations (LPE):

LPEs include weight, vital signs, a review of body systems to assess change from previous LPE and spleen measurement.

Bomedemstat (IMG-7289/MK-3543)

following the last assessment in the feeder study for as long as the patient continues to qualify for treatment, and at the Suspected Relapse, EoT, EoS and ET visits. Bone marrow sampling will not be repeated if performed in the prior 5 weeks.

 $^\dagger$ Aspirate sample should be optimally obtained within the first pull. Do not collect after a second pull attempt.

Local Laboratory Assessments: The following panels (Section 10.1.1 details analytes) will be performed as per below, and at the Transition Visit\*, Suspected Relapse, EoT, EoS and ET visits:

Genomic and Correlative Research Analyses: The following will be collected at the timepoints noted below, and (unless bone marrow was performed in the prior 5 weeks) at the Suspected Relapse, EoT, EoS and ET visits. Genomic mutant allele burden will be analyzed. Also, some or all of each sample may be placed in long-term storage for potential correlative research studies.

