# 3.6.1 Rationale for and Safety of the Proposed Bomedemstat Dose

In the Phase 2 study in MF patients (IMG-7289-CTP-102), the daily dose of bomedemstat needed by most patients to achieve a platelet count in the target range ( $50-75 \times 10^9/L$ ) is between 0.6 to 0.8 mg/kg/d with a dosing spectrum investigated of 0.4-1.5 mg/kg/d.

In the Phase 2 study in ET patients (IMG-7289-CTP-201), the daily dose of bomedemstat needed to reduce platelet counts into the target range (200-400 x  $10^9$ /L) is also currently between 0.6 to 0.8 mg/kg/d.

Imago BioSciences, Inc., a subsidiary of Merck & Co., Inc. Bomedemstat (IMG-7289/MK-3543)

To date, for both patient populations evaluated in clinical studies IMG-7289-CTP-102 and -201, the doses needed to reduce the platelet count to the target range do not appear to be correlated with the starting platelet count or antecedent hematologic history.

In the Phase 1 study in high-risk AML/ myelodysplastic syndrome (MDS) patients (IMG-7289-CTP-101), there was no maximum tolerated dose observed with doses up to 6 mg/kg/d.

Patients entering this study will have received bomedemstat for at least 6 months in their feeder study. All patients will be dosed with bomedemstat daily in the extension study, with dose-titration contingent on the Titration Assessment performed at every TP visit. Patients receiving their first extension study dose with no interruption in dosing will have a Titration Assessment performed at the Transition Visit to determine if a titration is needed. Patients requiring an interruption in dosing will have a Titration Assessment performed at the Transition Visit to determine if they will commence at the same daily dose of bomedemstat being taken at the conclusion of their feeder study or if a down-titration or dose hold is needed (up-titrations are not permitted).

The dose of bomedemstat needed to reduce platelets to the applicable target range is anticipated to be up to approximately 2 mg/kg once daily (QD); however, this is not the upper limit for titration purposes as the dose needed to achieve a therapeutic effect will vary among patients and may change over time. The upper limit for titration purposes is 6 mg/kg/d (**note:** this dose cannot be exceeded during the dose titration process).

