#### 8.2.1 Hematologic Toxicity

Hematologic values outside of the normal reference range are inherent features of MPNs and are expected effects of many therapeutic attempts to manage these diseases. MPN patients require doses of bomedemstat that are sufficient to reduce platelet counts and, to a lesser degree, absolute neutrophil counts. Any resulting reversible cytopenias can be managed clinically as needed with transfusions as well as broad-spectrum antibiotics, as *per* standard practice.

The effects of bomedemstat on normal myeloid hematopoiesis observed in non-clinical and clinical studies are expected; these are pharmacodynamic effects of LSD1 inhibition by bomedemstat, thus not regarded as adverse. Refer to the Investigator's Brochure for additional information.

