### 16.4 Revised IWG-MRT and ELN Response Criteria for MF

Response categories	Required criteria (for all response categories, benefit must last for ≥12 weeks to qualify as a response)
	Bone marrow:* Age-adjusted normocellularity; <5% blasts; ≤grade 1 MF † and
CR	Peripheral blood: Haemoglobin ≥100 g/L and <unl; 1="" 109="" <unl;="" and="" and<="" count="" l="" neutrophil="" platelet="" td="" x="" ≥="" ≥100=""></unl;>
CK	<unl; <2%="" and<="" cells‡="" immature="" myeloid="" td=""></unl;>
	Clinical: Resolution of disease symptoms; spleen and liver not palpable; no evidence of EMH
	Peripheral blood: Haemoglobin ≥100 g/L and <unl; 109/L and <unl; 109/L and</unl;></unl;>
	<unl; <2%="" and<="" cells‡="" immature="" myeloid="" td=""></unl;>
	Clinical: Resolution of disease symptoms; spleen and liver not palpable; no evidence of EMH or
PR	Bone marrow:* Age-adjusted normocellularity; <5% blasts; ≤grade 1 MF†, and peripheral blood: Haemoglobin ≥85 but <100
	g/L and <unl; 109/L and <unl; 10<sup="" <100="" but="" count="" platelet="" x="" ≥50,="">9/L and <unl; <2%="" immature<="" td=""></unl;></unl;></unl;>
	myeloid cells ‡ and
	Clinical: Resolution of disease symptoms; spleen and liver not palpable; no evidence of EMH
Clinical	The achievement of anaemia, spleen or symptoms response without progressive disease or increase in severity of anaemia,
improvement (CI)	thrombocytopenia, or neutropenia§
Anaemia response	Transfusion-independent patients: a ≥20 g/L increase in haemoglobin level¶
	Transfusion-dependent patients: becoming transfusion-independent(
	A baseline splenomegaly that is palpable at 5-10 cm, below the LCM, becomes not palpable** or
Spleen response	A baseline splenomegaly that is palpable at >10 cm, below the LCM, decreases by ≥50%**
	A baseline splenomegaly that is palpable at <5 cm, below the LCM, is not eligible for spleen response
	A spleen response requires confirmation by MRI or computed tomography showing ≥35% spleen volume reduction
Symptoms	A ≥50% reduction in the MPN-SAF TSS††
response	
	Appearance of a new splenomegaly that is palpable at least 5 cm below the LCM or
Progressive disease‡‡	A ≥100% increase in palpable distance, below LCM, for baseline splenomegaly of 5-10 cm or
	A 50% increase in palpable distance, below LCM, for baseline splenomegaly of >10 cm or

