	Leukaemic transformation confirmed by a bone marrow blast count of ≥20% or
	A peripheral blood blast content of $\geq$ 20% associated with an absolute blast count of $\geq$ 1 x 109/L that lasts for at least 2 weeks
Stable disease	Belonging to none of the above listed response categories
	No longer meeting criteria for at least CI after achieving CR, PR, or CI, or
Relapse	Loss of anaemia response persisting for at least 1 month or
	Loss of spleen response persisting for at least 1 month

EMH, extramedullary haematopoiesis (no evidence of EMH implies the absence of pathology- or imaging study-proven non-hepatosplenic EMH); LCM, left costal margin; UNL, upper normal limit.

\*Baseline and post-treatment bone marrow slides are to be interpreted at one sitting by a central review process.

†Grading of MF is according to the European classification Thiele et al. European consensus on grading bone marrow fibrosis and assessment of cellularity. It is

Imago BioSciences, Inc., a subsidiary of Merck & Co., Inc. Bomedemstat (IMG-7289/MK-3543)

underscored that the consensus definition of a CR bone marrow is to be used only in those patients in which all other criteria are met, including resolution of leukoerythroblastosis.

‡Immature myeloid cells constitute blasts + promyelocytes + myelocytes + metamyelocytes + nucleated red blood cells. In splenectomized patients, <5% immature myeloid cells are allowed.

§See above for definitions of anaemia response, spleen response, and progressive disease. Increase in severity of anaemia constitutes the occurrence of new transfusion dependency or a  $\geq 20$  g/L decrease in haemoglobin level from pretreatment baseline that lasts for at least 12 weeks. Increase in severity of thrombocytopenia or neutropenia is defined as a 2-grade decline, from pretreatment baseline, in platelet or absolute neutrophil count, according to the Common Terminology Criteria for Adverse Events (CTCAE) version 4.0. In addition, assignment to CI requires a minimum platelet count of  $\geq 25000 \times 10^9$ /L and absolute neutrophil count of  $\geq 0.5 \times 10^9$ /L. ¶Applicable only to patients with baseline haemoglobin of < 100 g/L.

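### Appendix 16.4 has no rule for intended platelet lowering, so an MF patient with a normal pretreatment count who reaches the stated platelet target can be denied Clinical Improvement, or scored as relapsed, without losing benefit

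*Combined protocol and SAP*

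**What the plan says.** **Response rule.** The Clinical Improvement row of Appendix 16.4 requires "The achievement of anaemia, spleen or symptoms response without progressive disease or increase in severity of anaemia", and the list goes on to thrombocytopenia and neutropenia. The footnote to that row says: "Increase in severity of thrombocytopenia or neutropenia is defined as a 2-grade decline, from pretreatment baseline, in platelet or absolute neutrophil count", graded "according to the Common Terminology Criteria for Adverse Events (CTCAE) version 4.0". The anaemia part of the footnote must last 12 weeks. The platelet part has no duration and no exception for a fall that the drug is meant to cause.

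**Relapse rule.** The first limb of relapse in the same table is "No longer meeting criteria for at least CI after achieving CR, PR, or CI, or". The other two limbs, loss of anaemia response and loss of spleen response, must persist for 1 month. The first limb has no such condition.

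**Platelet target.** Section 3.6.1 describes "the daily dose of bomedemstat needed by most patients to achieve a platelet count in the target range" in the MF feeder study, IMG-7289-CTP-102, and gives that range as 50-75 x10^9/L. For this extension, the synopsis says: "Titration targets and rules, specific to the underlying MPN, are detailed in the Study Reference Manual, Pharmacy Manual, and Appendix 16.1.3 and 16.1.4". That material is not visible in this copy.

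**Status of platelet lowering.** Section 8.2.1 says "MPN patients require doses of bomedemstat that are sufficient to reduce platelet counts and, to a lesser degree, absolute neutrophil counts". It classes the effects on normal myeloid cell production as pharmacodynamic and not adverse.

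**The concern.** The protocol treats a fall in platelets as the purpose of dosing in one place and as a toxicity that cancels a response in another. The visible text does not reconcile the two.

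Whether a patient is caught depends on the pretreatment platelet count and not on spleen, symptoms or haemoglobin. Two patients with the same benefit and the same on-treatment count can be scored differently because one began with a normal count and the other with a mildly low one.

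Response, including relapse, is a listed efficacy measure in the synopsis. Section 12.5.2 makes the extent and durability of effect, summarised from feeder-study baseline, the primary efficacy objective. At stake is whether those summaries can separate loss of benefit from platelet lowering that was intended.

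**Working it through.** The plan states no figure on this point, so there is nothing to reproduce. The check is a grade-shift count.

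**Inputs from the documents**
- CI is blocked by a 2-grade decline from pretreatment baseline (Appendix 16.4).
- The MF platelet band is 50-75 x10^9/L (Section 3.6.1, feeder study).

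**Assumptions, because the documents cite CTCAE v4.0 without printing it**
- Grade 0: at or above the lower limit of normal (LLN), tried at 100, 130 and 150.
- Grade 1: from c up to LLN. The limit c is tried from 50 to 90.
- Grade 2: from 50 up to c. Grade 3: from 25 up to 50.

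**Step 1: grade shift with c = 75.** Shift = on-treatment grade minus pretreatment grade. CI is blocked if the shift is 2 or more.

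| Pretreatment count (x10^9/L) | Pretreatment grade | Shift at 50, 60, 70, 74.9 | Shift at 75 |
|---|---|---|---|
| 150, 200 or 400 (any LLN tried) | 0 | 2 (CI blocked) | 1 |
| 120 (LLN 130 or 150) | 1 | 1 | 0 |
| 120 (LLN 100) | 0 | 2 (CI blocked) | 1 |
| 80 (any LLN tried) | 1 | 1 | 0 |
| 60 (any LLN tried) | 2 | 0 | -1 |

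The LLN decides who counts as grade 0. For a grade-0 patient the result is the same at every LLN tried.

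**Step 2: vary the limit that decides the result.** For a grade-0 patient, the share of the 50-75 band that blocks CI is (min(75, c) - 50) / 25.

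| c | 50 | 55 | 60 | 65 | 70 | 75 or more |
|---|---|---|---|---|---|---|
| Share of band | 0% | 20% | 40% | 60% | 80% | 100% |

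For example, c = 60 gives (60 - 50) / 25 = 40%. These are shares of the width of the band, not of patients.

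**Step 3: relapse, with c = 75.** Take a pretreatment count of 200. At 90 the patient is grade 1, a shift of 1, and can hold CI if the benefit lasts the required 12 weeks. At 62 the patient is grade 2, a shift of 2, and no longer meets CI. Read literally, the first limb then records a relapse although spleen and symptoms have not changed.

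**Step 4: other response routes.** As printed, complete remission and the first partial-remission route need platelets of at least 100. The second partial-remission route accepts 50 to below 100 and carries no 2-grade exclusion. It also needs haemoglobin of 85 to below 100 g/L, a normocellular marrow with fibrosis no higher than grade 1, resolved symptoms, and an impalpable spleen and liver. A patient who meets all of that still ranks at CI or better and is not in relapse.

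**A separate item.** The same footnote prints a CI platelet floor of 25000 x10^9/L, which is 1000 times the 25 x10^9/L MF interruption threshold in Section 8.2.2. It needs its own reconciliation. The check above sets it aside, and the conflict remains once the floor is corrected.

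**The case against.** **The deciding limit is not in the documents.** This stands. The result holds in full only if c is 75 or higher, and it disappears at 50. It must be stated as conditional.

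**The target is the feeder study's.** A reader might infer that this extension titrates MF patients to 50-75. The documents do not establish that. Patients are meant to transfer without a break in dosing, and the MF restart threshold in Section 8.2.2 is above 50. Both are compatible with the same target, but neither proves it.

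**Being at target does not always cost CI.** Also right. A count of exactly 75 is only 1 grade down when c = 75, patients with mildly low pretreatment counts keep CI, and the second partial-remission route is an exit. The relapse case needs an earlier qualifying period at a higher count. Patients enter after at least 6 months of dosing, so never being assigned CI may be the commoner outcome. The documents give no frequency for either.

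**These are published consensus criteria, and setting benefit against cytopenia is part of them.** This is a good reason not to redefine the main endpoint. It is no reason against showing what the qualifier does in a trial whose drug is meant to lower platelets.

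**Neutrophils are treated differently.** Section 8.2.1 also names a lesser, intended fall in neutrophils. The visible text gives no neutrophil target, so the same conflict cannot be shown there.

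**The analysis text is incomplete here.** The content of Section 12.4.2 is not visible, and Section 12.1 defers detail to a SAP. Spleen volume and symptoms are already separate measures. So one cannot say that the plan lacks any handling, only that none appears in the visible text.

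**Conclusion.** The conflict is real and conditional. If CTCAE grade 2 is 50 to below 75, an MF patient with a normal pretreatment count who reaches that range is denied CI unless the second partial-remission route is met. One who held CI at a higher count can be scored as relapsed under the first limb with no loss of spleen or symptom benefit. Across limits of 50, 60 and 75, the share of the band that blocks CI is 0%, 40% and 100%.

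A reader might go further on three points, and the documents support none of them.
- **A size for the understatement of the CI rate.** The documents give no pretreatment platelet distribution, no count of MF patients, no share at target and no response rate.
- **Extra bone marrow sampling through Suspected Relapse visits.** No visible text says what triggers such a visit, and sampling is waived if done in the prior 5 weeks.
- **Wrongful loss of treatment.** Continuation rests on progressive disease and tolerability (synopsis and Section 5.1), not on CI or relapse.

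The effect is therefore on the reporting of response and durability.

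**What to change.** Change the analysis plan only. No change to dosing or to the platelet target is implied.

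1. Keep the consensus CI and relapse definitions in Appendix 16.4 as the main version. State the CTCAE v4.0 platelet limits, the LLN and the pretreatment value used.
2. Prespecify in the SAP a supplementary CI rate and a supplementary first-limb relapse analysis that drop the platelet-decline qualifier and leave the anaemia and neutrophil qualifiers in place.
3. Flag each CI denial and each relapse that is due only to the platelet qualifier.
4. Tabulate anaemia, spleen and symptoms responses, and their durability, whether or not that qualifier is met.
5. Have the sponsor reconcile Appendix 16.4 with the platelet text in Sections 3.6.1 and 8.2.1 and with the titration targets that apply in this extension.

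The cost is SAP wording and one extra set of response tables. No new data are needed, and comparison with other trials is kept because the consensus version remains the main one.

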# **Efficacy**

In **all patients**, efficacy will be assessed by evaluation of:

- Constitutional symptoms measured by continued completion of the version of the MPN-SAF tool associated with the feeder study
- Formal measures of response, including relapse, and disease transformation
- Fibrosis score

In **MF patients**, efficacy will also be assessed by:

• Spleen volume reduction

In **ET patients**, efficacy will also be assessed by:

- Patient reported change in clinical status as measured by the PGIC
- Durability in the reduction of platelet counts in the absence of new thromboembolic events
- Durability in the reduction of white blood cell count
- Evaluation of the incidence of thromboembolic events

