## 12.5.2 Efficacy Data Analysis

The primary efficacy objective for this study is to measure the extent and durability of bomedemstat treatment effects on the exploratory endpoints including any impact of bomedemstat on the natural history of MF and ET. The long-term effects of bomedemstat will be examined by summarizing the exploratory endpoints from feeder study baseline through the extension study.

If applicable, progression free survival (PFS), event free survival (EFS), and overall survival (OS) will be calculated using the Kaplan-Meier method.

Additionally, for **MF Patients, s**pleen volume reduction will be assessed based on spleen volume measured by MRI (or CT where applicable).

Additionally, for **ET Patients**, the below endpoints, proportions and corresponding 95% confidence intervals will be based on the Clopper-Pearson method:

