# 16.5 Revised Response Criteria for ET: IWG-MRT and ELN Consensus 2013 (Barosi et al., 2013)

Response	Criteria
Kespolise	Crittia
Categories	

Complete Remission	
A	Durable* resolution of disease-related signs including palpable hepatosplenomegaly, large symptoms improvement, † AND
В	Durable* peripheral blood count remission, defined as: platelet count ≤400 x 10  /L, WBC count <10 x 10  /L, absence of leukoerythroblastosis, AND
С	Without signs of progressive disease, and absence of any hemorrhagic or thrombotic events, AND
D	Bone marrow histological remission defined as disappearance of megakaryocyte hyperplasia and absence of >grade 1 reticulin fibrosis.

A Durable* resolution of disease-related signs including palpable hepatosplenomegaly, and large symptoms improvement, AND  B Durable* peripheral blood count remission, defined as: platelet count ≤400 x 10°/L, WBC count <10 x 10°/L, absence of leukoerythroblastosis, AND  C Without signs of progressive disease, and absence of any hemorrhagic or thrombotic events, AND  D Without bone marrow histological remission, defined as the persistence of megakaryocyte hyperplasia.	Partial Remission	
platelet count ≤400 x 10  /L, WBC count <10 x 10  /L, absence of leukoerythroblastosis, AND  Without signs of progressive disease, and absence of any hemorrhagic or thrombotic events, AND  Without bone marrow histological remission, defined as the persistence of	A	0 01 1
thrombotic events, AND  Without bone marrow histological remission, defined as the persistence of	В	platelet count ≤400 x 10  /L, WBC count <10 x 10  /L, absence of
·	С	
	D	· · · · · · · · · · · · · · · · · · ·

Progressive	Transformation into PV, post-ET myelofibrosis, myelodysplastic syndrome or
Disease	acute leukemia‡

Any response that does not satisfy partial remission

Molecular response is not required for assignment as complete response or partial response. Molecular response evaluation requires analysis in peripheral blood granulocytes. Complete response is defined as eradication of a preexisting abnormality. Partial response applies only to patients with at least 20% mutant allele burden at baseline. Partial response is defined as  $\geq$ 50% decrease in allele burden.

WBC, white blood cell.

No Response

IWG-MRT criteria; for the diagnosis of myelodysplastic syndrome and acute leukemia, see WHO criteria.

\*Lasting at least 12 wk.

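### The platelet floor for Clinical Improvement in MF (Appendix 16.4) is printed about 1000 times too high, so read literally no MF patient can reach CI and the first relapse criterion is distorted

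*Combined protocol and SAP*

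**What the plan says.** Appendix 16.4 sets out the response criteria for MF. It defines CI as "The achievement of anaemia, spleen or symptoms response without progressive disease or increase in severity of anaemia", and likewise without worsening thrombocytopenia or neutropenia. The footnote to that row adds two blood-count conditions: "assignment to CI requires a minimum platelet count of $\geq 25000 \times 10^9$ /L" and an "absolute neutrophil count of $\geq 0.5 \times 10^9$ /L".

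Relapse in the same table has three alternative criteria. The first depends on CI: "No longer meeting criteria for at least CI after achieving CR, PR, or CI, or". The second is "Loss of anaemia response persisting for at least 1 month or", and the third is the same condition for the spleen response. Neither of those two refers to CI.

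The results are meant to be used. The synopsis, under Efficacy, lists "Formal measures of response, including relapse, and disease transformation" among the assessments in all patients. Section 12.5.2 states: "The primary efficacy objective for this study is to measure the extent and durability of bomedemstat treatment effects on the exploratory endpoints".

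**The concern.** CI is the lowest formal response category above stable disease, so its entry conditions should be no stricter than those for complete response (CR) or partial response (PR). The neutrophil floor follows that order. The platelet floor reverses it, and by so much that no patient could meet it.

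Two outputs are at stake. The CI rate would be empty by construction. The first relapse criterion would also change meaning: if CI cannot be met, holding at least CI reduces to holding CR or PR, which bears directly on durability of response.

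**Working it through.** **Inputs**

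| Quantity | Value | Source |
|---|---|---|
| CI platelet floor, as printed | 25000 × 10⁹/L | App. 16.4, CI footnote |
| CI neutrophil floor | 0.5 × 10⁹/L | App. 16.4, CI footnote |
| CR platelet floor; CR and PR neutrophil floor | 100 × 10⁹/L; 1 × 10⁹/L | App. 16.4, table |
| PR platelet floors (two routes) | 100, or 50 but below 100 × 10⁹/L | App. 16.4, table |
| ET remission ceiling | 400 × 10⁹/L | App. 16.5 |
| MF feeder-study platelet target | 50–75 × 10⁹/L | Section 3.6.1 |

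The CR and PR cells are badly laid out in the text copy that was read, but the figures are legible. The printed floor is a stated threshold, not a calculated one, so there is nothing to reproduce. The check is one of units and internal order.

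**Units.** 1 L = 10⁶ µL.
- As printed: 25000 × 10⁹/L ÷ 10⁶ = 25,000,000 per µL.
- If 25,000 was meant per µL: 25,000 × 10⁶ = 25 × 10⁹/L.
- Printed ÷ converted: 25000/25 = 1000.

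**Order within the table, as printed**
- Platelets, CI to CR: 25000/100 = 250.
- Platelets, CI to lower PR: 25000/50 = 500.
- Neutrophils, CI to CR or PR: 0.5/1 = 0.5.

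**Order with 25 × 10⁹/L**
- Platelets, CI to CR: 25/100 = 0.25.
- Platelets, CI to lower PR: 25/50 = 0.5.

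With 25, both counts make CI the more lenient category. As printed, only the platelet count breaks that order.

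**Scale elsewhere.** The printed floor is 25000/75 = 333 to 25000/50 = 500 times the MF target range. For scale only, it is 25000/400 = 62.5 times the ET ceiling, in a disease defined by high platelet counts. Values of 25, 50, 75, 100 and 400, and assumed extremes of 1000 and 2000 × 10⁹/L, all fail the printed floor and all meet 25.

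**Consequences if read literally**
1. No MF patient can be assigned CI, whatever the anaemia, spleen or symptoms response. Such patients appear to fall to stable disease, unless the component responses are themselves counted as categories.
2. A patient who no longer meets CR or PR but keeps a component response, and would otherwise qualify for CI, is counted as relapsed. A move from CR to PR is not affected.
3. A patient whose only response is in symptoms can never enter the first relapse criterion. The other two cover anaemia and spleen only, so loss of that response is never a relapse.

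**Not affected.** CR, both PR routes, the component responses, the second and third relapse criteria, and progressive disease do not use the floor. Continuation of treatment rests on progressive disease and tolerability (Section 5.1).

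**The case against.** The misprint itself is hard to dispute; the argument is over its consequence.

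- **A literal reading is unlikely.** An experienced assessor or programmer would see that the figure is impossible and read 25. This has force: a zero CI rate is the literal result, not a forecast. But a silent substitution is an undocumented change to an endpoint definition, and it may not be made the same way by everyone. The text needs correcting in either case.
- **The use of CI cannot be seen.** The exploratory endpoint list in Section 12.4.2 is not visible in the public copy, and Section 12.1 leaves detailed methods to the SAP. This also stands. The synopsis shows that response and relapse will be evaluated, but not how CI will be tabulated.
- **The relapse effect is narrow.** Over-counting requires a prior CR or PR. If the feeder-study target of 50–75 × 10⁹/L still applies (an assumption), a patient at target is below the floor of 100 for CR and for the first PR route. The missed relapses concern only patients with a symptoms response alone, and symptoms are reported separately. Both limits are fair. The same reasoning, however, leaves CI and the marrow-based PR route as the only formal categories open to a patient at that target, which makes the CI floor more important.
- **The efficacy analysis is exploratory, single-arm and unpowered.** True, and it limits how serious the point is. It does not make an unattainable threshold acceptable in a listed efficacy measure.

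Broken text extraction is an unlikely explanation. The number, exponent and unit are all legible, and the neutrophil floor in the same sentence came through correctly.

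**Conclusion.** The concern holds. The printed CI platelet floor is unattainable, contradicts the order of the other floors in Appendix 16.4, and is not corrected anywhere else in the document. The error is 1000-fold if the intended value is 25 × 10⁹/L. That value is an inference from the unit conversion and the neighbouring floors, and the source criteria were not available to confirm it.

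The literal CI rate is 0% in MF patients, and one of three relapse criteria is affected, in both directions. The number of patients concerned cannot be estimated from the documents. Confidence is high that the figure is wrong and lower on the practical effect, which depends on whether readers apply the figure or quietly replace it. The point should be fixed before response and relapse are derived, but it does not threaten the primary safety analysis.

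**What to change.** Correct the figure or the unit of the CI platelet floor in the Appendix 16.4 footnote, so that it is on the same scale as the other floors, after the sponsor has confirmed the value against the source criteria. State in the SAP that CI and the first relapse criterion are derived from the corrected value. If any response or relapse assessments have already been made, record which floor was used and re-derive them from the stored counts.

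As an editorial addition, cite the source of the MF criteria. The Appendix 16.4 heading names the consensus bodies but no paper, and the consensus response paper in Section 15 covers PV and ET.

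The cost is one corrected figure and one reference. No visits, data items, continuation rule or dosing text need to change for this.
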